1. PROTOCOL SUMMARY

SYNOPSIS

1.1 Justification for the proposed clinical study

In December, 2019, the Wuhan Municipal Health Committee in China identified an outbreak of viral pneumonia cases of unknown cause. Coronavirus RNA was quickly identified in some of these patients. This new coronavirus was called **SARS-CoV2** and the disease caused by that virus, **COVID-19**. To date, there are no approved therapeutic agents available for the specific treatment of coronavirus. In the absence of a known effective therapy in a global public health emergency, there is little evidence about the potential antiviral effect of chloroquine (CQ) in most coronaviruses, including SARS-CoV-1. We intend to investigate the efficacy and safety of treatment with CQ diphosphate in hospitalized patients with severe acute respiratory syndrome (SARS) within the scope of SARS-CoV2. Preliminary trials of CQ repositioning in the treatment of COVID-19 have been encouraged. As of the date of this version, there were 23 clinical trials registered with this theme, in progress in China (research conducted on *clinicaltrials.gov* and *Chictr*). However, with the reduction in the number of cases in the country, the chance of conclusions that may be used for treatment in other continents is low.

1.2 Study design

This is a randomized, double-blind, placebo-controlled clinical trial. A total of 440 individuals aged between 18 and 80 years, diagnosed with severe respiratory disease, hospitalized in one of the hospitals participating in the study, with suspected SARS-CoV2, will be randomized into two treatment groups at a 1:1 ratio, with group 1 receiving CQ 600mg twice a day for 10 days and group 2 receiving CQ 450mg twice a day on the first day and 450mg once a day for the next 4 days. In order to blind study team and participants, placebo tablets will be used to standardize group 2 treatment for 10 days as group 1. According to the Contingency Plan for coping with Covid-19 in Amazonas, the Hospital e Pronto Socorro Delphina Rinaldi Abdel Aziz Hospital (HPSDRAA), in the north of Manaus, is the reference unit for the admission of serious cases of the new virus. The unit currently has 50 ICU beds, which can increase to a

capacity of 150 ICU beds, 335 beds in total. The hospital also has trained multiprofessional human resources and adequate infrastructure to serve this population. It is the largest hospital in the country dedicated exclusively to the admission of patients with COVID-19, and is publically-privately managed.

1.3 Sample calculation

The sample for the primary outcome (reduction in lethality) was calculated assuming a 20% lethality incidence in critically ill patients not using CQ (historical control) and that both arms of CQ would be equally able to reduce lethality by at least 50%. Thus, considering a test of differences in proportions between 2 groups of the same size, 80% power and 5% alpha, 394 participants were needed (197 per group). Adding 10% of losses, the final sample of 440 participants was obtained. Sample calculation was performed in the R statistical package (v3.6.1), with the functions implemented in the TrialSize and gsDesign packages.

1.4 Study objectives

1.4.1 Primary objective

Assess whether the therapeutic regimen of group 1 reduces mortality by 50% in the study population compared to group 2.

1.4.2 Secondary objectives

- 1. Assess mortality on days 7, 14 and 28 after hospitalization;
- 2. Evaluate indicators of clinical worsening (use of supplemental oxygen, ICU stay, length of stay in the ICU, length of hospital stay, need for intubation and time on mechanical ventilation, radiological alterations and time to improve the radiological and resonance pattern);
- 3. Assess the percentage of SARS-CoV2 detection in oropharyngeal swab, nasal and blood swab samples on days 1, 3, 5, 8, 11, 14 and 28, in the study population;

- 4. Quantify the virus that causes SARS-CoV2 in oropharyngeal swab, nasal and blood swab samples on days 1, 3, 5, 8, 11, 14 and 28, in the study population;
- 5. Cumulative incidence of adverse events (AEs);
- 6. Cumulative incidence of grade 3 and 4 serious adverse events (SAEs);
- 7. Discontinuation or temporary suspension of treatment (for any reason);
- 8. Alterations in white cell count, hemoglobin, platelets, creatinine, glucose, total bilirubin, ALT and AST over time;
- 9. In case of mortality, describe organic alterations via autopsy.

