1.8 Study population

Groups 1 and 2: Hospitalized adult patients (≥18 years old) with severe respiratory syndrome.

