1.12 Table 1: Schedule for evaluation throughout the study

| Description of the procedures according | D0* | D1∞ | D2 | D3 | D4 | D5 | D6 | D7 | D8 | D9 | D10 | D11 | Dx | D14# | D28# |
|--|-----|-----|-----|-----|-----|-----|-----|-----|-----|-----|-----|-----|-----|------|------|
| to the protocol $^{\mu}$ | D0 | Di | D2 | D3 | | | 20 | 2, | | | DIO | | | | D20 |
| Application of ICF ^t | X | | | | | | | | | | | | | | |
| Review of eligibility criteria ^a | X | | | | | | | | | | | | | | |
| Randomization ^b | X | | | | | | | | | | | | | | |
| Demography, medical history, including comorbidities (HAS, DM, dG6PD) and coinfections (HIV, TB, hepatitis) ^c | X | | | | | | | | | | | | | | |
| Physical exam ^d | X | | | | | | | | | | | | | | |
| Clinical evaluation ^e | X | X | X | X | X | X | X | X | X | X | X | Х | X | X | X |
| Evaluation of concomitant medication ^f | X | X | X | X | X | X | X | X | X | X | X | X | X | X | X |
| 12-lead ECG ^g | X | X | X | X | X | X | X | X | Х | X | X | X | X | X | X |
| Blood sample collection for hematology and biochemistry ^h | Х | (x) | (x) |
| Blood sample collection for virology and storage ⁱ | Х | Х | | X | | Х | | X | | | | Х | X | Х | Х |
| Oropharyngeal Swab and Nasal Swab | Х | X | | X | | X | | X | | X | | Х | X | X | X |
| Record of adverse events (serious and non-serious) ^j | X | X | X | X | Х | Х | Х | X | X | X | X | X | X | X | Х |
| Assessment of the primary outcome ^k | | | | | | | | X | | | | | | X | X |
| Record of secondary outcomes ¹ | | X | X | X | X | X | X | X | X | X | X | X | X | X | Х |

Version_2.0_23march2020

| Respiratory evaluation ^m | (x) |
|--------------------------------------|-----|-----|-----|-----|-----|-----|-----|-----|-----|-----|-----|-----|-----|-----|-----|
| Radiological evaluation ⁿ | (x) |

- μ All data from the study procedures will be collected and entered into the RedCap system;
- * Screening and Randomization may occur on the same day. All procedures must be performed before the study intervention;
- ∞ Evaluations and collections should take place after 24 hours of administration of the investigational product;
- τ The Informed Consent Form will be obtained by the study nurse directly from the participant, or in case of no possibility of this occurring (example: loss of level of consciousness), from a family member or legal guardian.
- Dx Days of hospitalization after completion of treatment;

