- # Participant may be hospitalized or discharged. In the latter case, there will be no outpatient return visit and the main outcome will be assessed by telephone. Note: all procedures will be performed during the hospitalization period and will be interrupted if the participant is discharged;
- a Inclusion/exclusion criteria will be fully assessed at visit D1, prior to inclusion. The diagnosis of SARS-CoV2 will occur a posteriori.
- b Randomization will take place in blocks of 4 with 110 participants each. There will be interim reviews when 25%, 50% and 75% of participants are included;
- c A complete medical history will be obtained prior to randomization to include assessments of cardiovascular, metabolic (for example, Type I or II diabetes mellitus), psychiatric (such as depression), renal (such as nephrolithiasis, nephropathy, renal failure) and bone disorders;
- d Physical examination will consist of evaluation of vital signs (heart rate, respiratory rate, systolic, diastolic and mean blood pressure, peripheral oxygen saturation) and signs and symptoms present;
- e Assessments to highlight any visual and/or mental alterations resulting from chloroquine;
- f Avoid administration of other drugs known to prolong the QT interval (ie quinolones, macrolides, ondansetron), as well as various antiarrhythmic, antidepressant and antipsychotic drugs; Avoid administration of other drugs known to prolong the QT interval (ie quinolones, macrolides, ondansetron), as well as various antiarrhythmic, antidepressant and antipsychotic drugs;
- g A 12-lead ECG will be performed in a semi-supine position after resting for at least 5 minutes. The intention is to exclude the development of prolongation in the QT interval or bradycardia;
- h Blood samples will be collected to assess the COVID-19 infection and perform laboratory tests requested by the doctor. In the case of Manaus, the evaluation of the infection by COVID-19 will take place at LACEN-FVS and the others will take place at the Delphina Rinaldi Abdel Aziz Hospital and A & E. In Niterói-RJ all tests will be performed at the hospital. In Mato Grosso do Sul, the evaluation of infection by COVID-19 will take place at LACEN-MS and any others will take place at participating hospitals;

Version 2.0 23march2020

- i Blood samples will be collected for storage in a biorepository for further evaluation of the immune response profile;
- j Evaluated according to the DAIDS table for clinical and laboratory events;

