4. STUDY DESIGN

4.1 General design of the project

This is a double-blind, randomized, placebo-controlled clinical trial. A total of 440 individuals, aged 18 years or older, diagnosed with severe respiratory disease, without contraindications to CQ, hospitalized in the HPSDRAA, with suspected SARS-CoV2, will be randomized into two treatment groups, in the ratio of 1:1, with group 1 receiving CQ 600mg twice a day for 10 days or group 2 receiving CQ 450mg twice a day on the first day and 450mg once a day the following 4 days. In order to blind study team and participants, placebo tablets will be used to standardize group 2 treatment for 10 days as group 1. Both groups will receive drugs via oral administration or nasogastric tube in case of orotracheal intubation. Chloroquine and placebo will be donated by Farmanguinhos on an emergency basis. Clinical and laboratory data during hospitalization will be used to assess the efficacy and safety outcomes. Blood samples and oropharyngeal swabs (OPS) will be obtained on days 1, 3, 5, 7, 14 and 28 (while hospitalized).

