5.2 Inclusion criteria

- 1. Adult aged 18 years or older, at the time of inclusion (children under 18 will not be included due to the recognized lower lethality in previous published studies, and the difficulty of consent in the context of a public health emergency);
- 2. Hospitalized;
- 3. And presents with clinical suspicion of COVID-19 AND:
- Respiratory rate > 24 bpm AND/OR
- Heart rate > 125 bpm (in the absence of fever) AND/OR
- Peripheral oxygen saturation <90% in ambient air AND/OR
- Shock (defined as MAP <65 mmHg, requiring a vasopressor or oliguria or lowering the level of consciousness)

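### The virological objectives count all suspected cases, are sampled only while patients remain in hospital, and list days that do not match the sampling schedule

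*Protocol*

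**What the plan says.** Secondary objectives 3 and 4 in Protocol section 1.4.2 concern the percentage with SARS-CoV2 detected and the quantity of virus, in "samples on days 1, 3, 5, 8, 11, 14 and 28, in the study population". Table 2 (section 3) repeats that population with a different day list. It also names absence of virus in respiratory secretions as an outcome, without requiring an earlier positive test.

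Section 1.8 describes the population as "Hospitalized adult patients (≥18 years old) with severe respiratory syndrome". The fuller entry criteria in section 5.2 add only suspicion: "And presents with clinical suspicion of COVID-19 AND". Footnote a to Table 1 (section 1.12) states: "The diagnosis of SARS-CoV2 will occur a posteriori".

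On sampling after discharge, the # footnote to Table 1 says that "all procedures will be performed during the hospitalization period and will be interrupted if the participant is discharged", and that "there will be no outpatient return visit and the main outcome will be assessed by telephone". Section 4.1 schedules blood and oropharyngeal swabs "on days 1, 3, 5, 7, 14 and 28 (while hospitalized").

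The footnote attached to D1 in Table 1 reads: "Evaluations and collections should take place after 24 hours of administration of the investigational product". The footnote marked * places screening and randomisation procedures before the intervention, so D0 is the pre-dose time point.

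**The concern.** A possible antiviral effect is the rationale for testing chloroquine, and these two objectives are where it would show. Three features weaken what they can say.

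- **Denominator.** A patient who never had the virus is negative throughout. With no condition of earlier positivity, that patient looks the same as one who cleared the virus. For viral quantity, uninfected patients add undetectable values.
- **Who is sampled.** From the first discharge or death onward, samples come from a shrinking group formed after randomisation. By days 14 and 28 it is limited to patients alive and still admitted. If dose affects death or length of stay, the groups sampled in the two arms differ for that reason alone.
- **Days.** The objective names a day with no scheduled virology sample and leaves out the one sample taken before treatment.

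**Working it through.** **The plan's own figure.** The virological objectives have no sample size. The only stated figure is for mortality: 20% versus 10%, two-sided 5%, 80% power. The unpooled formula gives (1.960 + 0.842)² × (0.20×0.80 + 0.10×0.90) / 0.10² = 196.2, so 197 per group. Then 394 / 0.90 = 438, against the stated 440 (110 blocks of 4). It reproduces, and nothing below alters it.

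**Dilution.** The uninfected share q is an assumption, because the Protocol gives no confirmation rate. If d is detection among the infected, and the uninfected all test negative, detection over everyone is d × (1 − q). With an illustrative 60% versus 40% among the infected:

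- q = 0.10: 0.60 × 0.90 = 54% versus 0.40 × 0.90 = 36%; the difference falls from 20 to 18 points.
- q = 0.30: 0.60 × 0.70 = 42% versus 0.40 × 0.70 = 28%; the difference falls to 14 points.

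The cost in power, with 50% versus 35% assumed among the infected, 220 randomised per arm, two-sided 5% and the pooled normal approximation:

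| Infected fraction | Detection, all randomised | Power, all randomised | Power, infected only |
|---|---|---|---|
| 0.9 | 45.0% vs 31.5% | 0.83 | 0.86 |
| 0.8 | 40.0% vs 28.0% | 0.76 | 0.82 |
| 0.7 | 35.0% vs 24.5% | 0.67 | 0.76 |
| 0.6 | 30.0% vs 21.0% | 0.58 | 0.70 |

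Restricting to infected patients gives higher power despite fewer patients. The calculation makes no allowance for samples lost to discharge or death.

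**Selection by discharge.** All inputs are assumed. In both arms half the infected are severe, all still admitted on day 14 and 60% positive; the other half are mild and 20% positive. True detection is 0.5 × 0.60 + 0.5 × 0.20 = 40% in each arm. Let 30% of mild patients be discharged in one arm and 70% in the other:

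- 30% discharged: (0.30 + 0.5 × 0.70 × 0.20) / (0.50 + 0.35) = 0.37 / 0.85 = 43.5%.
- 70% discharged: (0.30 + 0.5 × 0.30 × 0.20) / (0.50 + 0.15) = 0.33 / 0.65 = 50.8%.

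An apparent difference of about 7 points arises with no virological effect.

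**Days, side by side.**

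| Place in the Protocol | Virology days |
|---|---|
| Section 1.4.2, objectives 3 and 4 | 1, 3, 5, 8, 11, 14, 28 |
| Table 2 (section 3) and section 4.1 | 1, 3, 5, 7, 14, 28 |
| Table 1, blood for virology | D0, 1, 3, 5, 7, 11, Dx, 14, 28 |
| Table 1, swabs | D0, 1, 3, 5, 7, 9, 11, Dx, 14, 28 |

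Day 8 is named only in section 1.4.2. Day 11 is in section 1.4.2 and Table 1 but not in Table 2 or section 4.1. D0 is in Table 1 only.

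**The case against.** The best defence is that the denominator problem is inferred. No sentence says that uninfected patients are to be counted as negative, and a statistical analysis plan that is not at hand may define a baseline-positive set and the handling of discharge and death. The first part stands as a limit on the claim. The second does not remove it: the objectives name their population, so a narrower set would depart from them, and no analysis plan can supply a day 8 sample.

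Second, the objectives ask only to assess and quantify. Section 10.1 names no virological test, and the synopsis outcome list has no virological item. The restriction to inpatients is openly stated. A reader might infer that the plan presents day 14 and 28 virology as a randomised comparison; the text does not. The fault is that objectives set over the study population up to day 28 can be met at those days only in remaining inpatients.

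Third, a reader might conclude that the plan has no baseline. It has one: D0 blood and swabs are scheduled before treatment. Nor is D1 wholly clear. Its footnote makes it post-dose, while footnote a places the eligibility review at D1, before inclusion. What stands is that no objective uses D0.

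Two further inferences fail.

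- **Chance imbalance as a separate bias.** With 220 per arm, the standard deviation of the between-arm difference in the uninfected share is √(2q(1 − q)/220): 2.9 points at q = 0.1 and 4.4 at q = 0.3. It enters multiplied by the detection rate, so at 40% to 60% detection it is roughly 1 to 3 points. This is ordinary sampling error.
- **Damage to the mortality analysis.** The planned effect in sections 5.1 and 10.2 is stated for severe respiratory patients. Dilution there would require assuming that the effect exists only in the infected, and the main outcome is still obtained by telephone after discharge.

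**Conclusion.** The point holds for secondary objectives 3 and 4 and the matching Table 2 outcomes. The denominator mixes clearance with never having been infected. It multiplies any between-arm difference by the infected fraction: 20 points become 18 or 14 on the assumed 10% to 30% uninfected. Results after discharges and deaths begin, above all on days 14 and 28, describe patients alive and still admitted. The day lists contradict each other whatever is assumed.

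The conflict in days and the stop at discharge are read directly from the text. The sizes rest on assumed infection, detection and discharge rates and are illustrations only. The primary endpoint and its sample size are untouched, so this should be corrected but does not threaten the main result.

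**What to change.** - In sections 1.4.2 and 3, define the virological objectives and outcomes in participants RT-PCR positive on the pre-dose D0 sample, with D0 as baseline. D0 status is fixed before treatment, so comparing arms within this subset keeps the benefit of randomisation.
- Reconcile the days in sections 1.4.2, 3 and 4.1 with Table 1: blood on D0, 1, 3, 5, 7, 11, Dx, 14 and 28; swabs on the same days plus D9.
- Base any between-arm virological comparison on an early in-treatment day. State that this reduces selection by death and discharge but does not remove it.
- Label day 14 and 28 virology as descriptive in inpatients.
- Keep all randomised patients for the primary mortality analysis. Day-28 mortality in D0-positive patients is an optional supportive addition.

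The cost is mainly wording, because D0 blood and swabs are already scheduled. The Protocol should say explicitly that the D0 sample is tested by RT-PCR, since it says only that diagnosis follows later. The price is a smaller virology denominator and the exclusion of patients with a false-negative D0 test.

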1.5 Study outcomes

1.4.1 Primary outcome

- 50% mortality reduction by day 28.

1.4.2 Secondary outcomes

- 1. Mortality on days 7 and 14;
- 2. Clinical status of the study subject on days 14 and 28;
- 3. Daily clinical status during hospitalization;
- 4. Time on supplemental oxygen (if applicable);
- 5. Time on mechanical ventilation (if applicable);
- 6. Length of hospitalization;
- 7. Data and cause of death (if applicable);
- 8. Incidence of adverse events;

9. Incidence of serious adverse events (grades 3 and 4).

1.6 Inclusion criteria

- 1. Adult 18 years of age or older, at the time of inclusion (children under 18 will not be included due to the recognized lower lethality in previous published studies, and the difficulty of consent in the context of a public health emergency);
 - 2. Hospitalized;
 - 3. And presents with:
- Respiratory rate > 24 bpm AND/OR
- Heart rate > 125 bpm (in the absence of fever) AND/OR
- Peripheral oxygen saturation <90% in ambient air AND/OR
- Shock (defined as MAP <65 mmHg, requiring a vasopressor or oliguria or lowering the level of consciousness)

1.6 Exclusion criteria

(Does not apply).

1.7 Study phase

Phase IIb.

1.8 Study population

Groups 1 and 2: Hospitalized adult patients (≥18 years old) with severe respiratory syndrome.

1.9 Study location

- Delphina Rinaldi Abdel Aziz Hospital and A & E (HPSDRAA), Manaus, AM, Brazil
- Hospital Santa Júlia, Manaus, AM, Brazil
- Fundação Municipal de Saúde, Niterói-RJ, Brazil

- Hospital Universitário Maria Aparecida Pedrossian, Campo Grande-MS, Brazil
- Hospital Regional de Mato Grosso do Sul, Campo Grande-MS, Brazil

1.11 Study duration

The study will last for the period of appearance of cases (expected between April 6th and August 31st, 2020), or until the sample is completed, or until the interim analysis shows a clear benefit or harm. The period was calculated based on our modeling of the number of cases in Manaus, as shown below.

To obtain a possible scenario of infected by COVID-19 in the city of Manaus, we used simulation using the SIR model (Susceptible, Infected and Recovered) to have an idea of the probable period when we will have the peak of infection in the city of Manaus. The parameters used for the modeling were as follows: R0 = 2.5, from studies in China; the Susceptible rate 0.92, the infected rate 0.01 and the Recovered rate 1/14. The first case found in Manaus was diagnosed on March 11^{th} , 2020.

The obtained result can be seen in the graph below.

1.11.1 Follow-up duration

An individual will complete the study in 28 days, starting from their inclusion.

1.11.2 Safety

Given the severity of the disease COVID-19, there is no study pre-specifying criteria for interrupting follow-up. The protocol team will review blind AE/SAE data every 2 weeks. If there is a worrying number of unexpected AEs, the researcher will request a review of the non-hidden security data in an ad hoc meeting with the external security monitoring committee, which should take place in real time, via videoconference.

1.12 Table 1: Schedule for evaluation throughout the study

| Description of the procedures according | D0* | D1∞ | D2 | D3 | D4 | D5 | D6 | D7 | D8 | D9 | D10 | D11 | Dx | D14# | D28# |
|--|-----|-----|-----|-----|-----|-----|-----|-----|-----|-----|-----|-----|-----|------|------|
| to the protocol $^{\mu}$ | D0 | Di | D2 | D3 | | | 20 | 2, | | | DIO | | | | D20 |
| Application of ICF ^t | X | | | | | | | | | | | | | | |
| Review of eligibility criteria ^a | X | | | | | | | | | | | | | | |
| Randomization ^b | X | | | | | | | | | | | | | | |
| Demography, medical history, including comorbidities (HAS, DM, dG6PD) and coinfections (HIV, TB, hepatitis) ^c | X | | | | | | | | | | | | | | |
| Physical exam ^d | X | | | | | | | | | | | | | | |
| Clinical evaluation ^e | X | X | X | X | X | X | X | X | X | X | X | Х | X | X | X |
| Evaluation of concomitant medication ^f | X | X | X | X | X | X | X | X | X | X | X | X | X | X | X |
| 12-lead ECG ^g | X | X | X | X | X | X | X | X | Х | X | X | X | X | X | X |
| Blood sample collection for hematology and biochemistry ^h | Х | (x) | (x) |
| Blood sample collection for virology and storage ⁱ | Х | Х | | X | | Х | | X | | | | Х | X | Х | Х |
| Oropharyngeal Swab and Nasal Swab | Х | X | | X | | X | | X | | X | | Х | X | X | X |
| Record of adverse events (serious and non-serious) ^j | X | X | X | X | Х | Х | Х | X | X | X | X | X | X | X | Х |
| Assessment of the primary outcome ^k | | | | | | | | X | | | | | | X | X |
| Record of secondary outcomes ¹ | | X | X | X | X | X | X | X | X | X | X | X | X | X | Х |

Version_2.0_23march2020

| Respiratory evaluation ^m | (x) |
|--------------------------------------|-----|-----|-----|-----|-----|-----|-----|-----|-----|-----|-----|-----|-----|-----|-----|
| Radiological evaluation ⁿ | (x) |

- μ All data from the study procedures will be collected and entered into the RedCap system;
- * Screening and Randomization may occur on the same day. All procedures must be performed before the study intervention;
- ∞ Evaluations and collections should take place after 24 hours of administration of the investigational product;
- τ The Informed Consent Form will be obtained by the study nurse directly from the participant, or in case of no possibility of this occurring (example: loss of level of consciousness), from a family member or legal guardian.
- Dx Days of hospitalization after completion of treatment;
- # Participant may be hospitalized or discharged. In the latter case, there will be no outpatient return visit and the main outcome will be assessed by telephone. Note: all procedures will be performed during the hospitalization period and will be interrupted if the participant is discharged;
- a Inclusion/exclusion criteria will be fully assessed at visit D1, prior to inclusion. The diagnosis of SARS-CoV2 will occur a posteriori.
- b Randomization will take place in blocks of 4 with 110 participants each. There will be interim reviews when 25%, 50% and 75% of participants are included;
- c A complete medical history will be obtained prior to randomization to include assessments of cardiovascular, metabolic (for example, Type I or II diabetes mellitus), psychiatric (such as depression), renal (such as nephrolithiasis, nephropathy, renal failure) and bone disorders;
- d Physical examination will consist of evaluation of vital signs (heart rate, respiratory rate, systolic, diastolic and mean blood pressure, peripheral oxygen saturation) and signs and symptoms present;
- e Assessments to highlight any visual and/or mental alterations resulting from chloroquine;
- f Avoid administration of other drugs known to prolong the QT interval (ie quinolones, macrolides, ondansetron), as well as various antiarrhythmic, antidepressant and antipsychotic drugs; Avoid administration of other drugs known to prolong the QT interval (ie quinolones, macrolides, ondansetron), as well as various antiarrhythmic, antidepressant and antipsychotic drugs;
- g A 12-lead ECG will be performed in a semi-supine position after resting for at least 5 minutes. The intention is to exclude the development of prolongation in the QT interval or bradycardia;
- h Blood samples will be collected to assess the COVID-19 infection and perform laboratory tests requested by the doctor. In the case of Manaus, the evaluation of the infection by COVID-19 will take place at LACEN-FVS and the others will take place at the Delphina Rinaldi Abdel Aziz Hospital and A & E. In Niterói-RJ all tests will be performed at the hospital. In Mato Grosso do Sul, the evaluation of infection by COVID-19 will take place at LACEN-MS and any others will take place at participating hospitals;

Version 2.0 23march2020

- i Blood samples will be collected for storage in a biorepository for further evaluation of the immune response profile;
- j Evaluated according to the DAIDS table for clinical and laboratory events;
- k Evaluated and recorded in the hospital's electronic medical record and inserted in the RedCAP system;
- 1 Evaluated and recorded in the hospital's electronic medical record and inserted in the RedCAP system;
- m If a patient needs it, orotracheal intubation will be performed and the parameters of the mechanical ventilator will be recorded daily;
- n Radiology, tomography or nuclear magnetic resonance exams will be performed according to medical request and New Coronavirus Treatment Protocol (2019-nCOV)
- () denotes optional procedure, to be evaluated by the health professional according to clinical needs

[figure not shown]
Version 2.0 23march2020

